The number of hospitalizations will be analyzed similarly as the infections, i.e. number of hospitalizations, number and percentages of hospitalized subjects, incidence rates of hospitalizations for the time periods described above. The duration of hospitalizations will be described by descriptive statistics for continuous variables based on the number of hospitalizations. Subjects who are hospitalized in one analysis period and discharged from the hospital in the subsequent analysis period will be counted for the full hospitalization period (i.e. from admission to discharge) in the analysis period where they were hospitalized. All hospitalizations will also be presented in a data listing.

For subjects <18 years of age, height-for age and weight-for age and for patients between 24 months and 18 years of age, BMI-for age will be presented by z-scores at baseline and each intermediate collection time-point. Z-scores will be calculated programmatically based on reported age, gender, height and weight.¹ Z-scores and changes from baseline of z-scores to each visit (at which height and weight are assessed) will be summarized using descriptive statistics.

¹ http://www.cdc.gov/nccdphp/dnpao/growthcharts/resources/sas.htm

Overall survival will be analyzed by a Kaplan-Meier analysis. Kaplan-Meier survival curves will be plotted by subject status. Subjects who are alive at the end of the observational period will be counted as a censored observation. Observational period is the time from initiation of Revcovi until the date of study completion or study discontinuation (calculated as: date of study completion or study discontinuation – date of treatment initiation + 1 day) or from treatment initiation until the date of death, for subjects who die (calculated as date of death – date of treatment initiation + 1 day). Date of study completion or date of study discontinuation will be used as reported on the Patient Disposition page in the eCRF. For subjects transitioning from the STP-2279-002 study, overall survival will be calculated based on the date of the first dose of Revcovi in the STP-2279-002 study. If it is known that the subject died, but the date of death is unknown, it will be assumed that the subject died the day after their last assessment (whatever has been entered as last available date to the database, e.g. date of laboratory value, onset or resolution date of an AE, date of study discontinuation).

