14. PROGRAMMING SPECIFICATIONS

- The following algorithm should be used to estimate adverse event start dates for which only partial information is known. To conservatively assign start dates as early as possible, the first day on study drug is the reported start date of Revcovi in the CLI-06814AA1-01 study.
 - Missing day and month
 - If the year is the same as the year of first day on drug, then the day and month of the start date of drug will be assigned to the missing fields.
 - If the year is prior to the year of first day on drug, then December 31 will be assigned to the missing fields.
 - If the year is after the year of first day on drug, then January 01 will be assigned to the missing fields.
 - Missing month only
 - Treat day as missing and replace both month and day according to the above procedure.
 - o Missing day only
 - If the month and year are the same as the year and month of first day on drug, then the start date of drug will be assigned to the missing day.
 - If the month and year are before the year and month of first day on drug, then the last day of the month will be assigned to the missing day.
 - If the month and year are after the year and month of first day on drug, then the first day of the month will be assigned to the missing day.

If the resultant imputed start date is after the AE stop date (and the AE stop date is complete), the imputed start date will be reset to the AE stop date.

- Adverse events with partially missing stop dates and the outcome is "Resolved" or "Resolved with sequelae" will have stop dates imputed as follows:
 - *year is missing* date left missing.
 - o month is missing impute 'December'.
 - o *day is missing* impute 'last date of that month'.

- It is assumed that for the start and stop date of Revcovi, at least month and year are known. If day is missing, it will be imputed by the first of the month, if necessary.
- Partially missing start dates for Adagen pre-treatment (Adagen transitioning patients) will be imputed as follows:
 - Day is missing impute 01 of the month
 - Day and month is missing: impute 01July.
- It is assumed that at least month and year is known for the QoL questionnaires, physical examinations, vital signs, and other laboratory data. If the day is missing, day will be imputed by the 15th of the month. If month and/or year is missing, the records will be excluded from all analyses.
- Partially missing dates for the diagnosis of ADA-SCID will be imputed as follows:

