 - Year is missing impute with date of birth
 - Month is missing and year is available impute by 01 January. If the imputed date is prior to the date of birth, impute date of birth.
 - Day is missing impute first day of month. If this imputed date is prior to the date of birth, impute date of birth.
- Complete dates for concomitant medications with missing or partially missing start dates will be imputed, if necessary, using the same algorithm described for adverse event onset dates. If the stop date is missing or partially missing and the "ongoing" variable is indicated as 'no', the imputation rule is applied in the following order:
 - *year is missing* the medication will be considered to have been received at all periods after that period determined by the start date. Date is left missing.
 - o month is missing impute 'December'.
 - o *day is missing* impute 'last date of that month'.
- The following algorithm should be used, when necessary, to calculate a start date that is partially missing for medical history:
 - missing day and month January 01 will be assigned to the missing fields.
 - *missing month only* treat day as missing and replace both month and day according to the above procedure.
 - *missing day only* assign first of the month to the missing day.
- Partially missing stop dates will be imputed as:
 - *year is missing*, no imputation. Date left missing.

- *month is missing and year is prior to year of first dose of study medication*impute 'December'.
- month is missing and year the same as the year of the first dose of study medication impute same month as in start date.
- \circ day is missing: impute 'last date of that month'. If this results in a date \geq the date of the first dose of study medication, impute day as the day prior to the first dose of study medication.
- Partial missing death dates will be imputed in the same way as adverse event start dates.
- Date imputations will be applied to the process of assigning study day and should be retained in the analysis datasets, but the data listings should display the original, partially missing dates.
- Adverse event summary tables will only include treatment-emergent AEs. However, listings will include all AEs (i.e., treatment-emergent and non treatment-emergent AEs) with the non treatment-emergent AEs flagged.

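### Partial death dates follow the AE-onset rule, which has no floor at the last recorded assessment and conflicts with the SAP's own rule for unknown death dates

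*SAP*

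**What the plan says.** SAP section 14 covers incomplete death dates in one line: "Partial missing death dates will be imputed in the same way as adverse event start dates". The algorithm it points to, earlier in the same section, has a stated aim, "To conservatively assign start dates as early as possible", and a stated reference date: "the first day on study drug is the reported start date of Revcovi in the CLI-06814AA1-01 study". Four of its branches matter for a death after first dose:

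- Day and month missing, year of first dose: "then the day and month of the start date of drug will be assigned to the missing fields".
- Day and month missing, later year: "If the year is after the year of first day on drug, then January 01 will be assigned to the missing fields".
- Day missing, month of first dose: "then the start date of drug will be assigned to the missing day".
- Day missing, later month: "then the first day of the month will be assigned to the missing day".

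The only bound is a cap at a complete AE stop date, which can only move the date earlier. Section 14 carries imputed dates into study-day assignment and the analysis datasets, while listings show the original partial date.

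SAP section 7.2.3 has a different rule for a subject known to have died on an unknown date: "it will be assumed that the subject died the day after their last assessment". It takes the last assessment to be the latest date of any kind in the database, including a laboratory, AE or study discontinuation date. Overall survival for a death runs from treatment initiation to the date of death, counting both days. For STP-2279-002 participants it starts at the first dose in that earlier study.

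**The concern.** Early dating has a purpose for adverse events: an event of uncertain onset is counted as treatment-emergent rather than lost. It has no such purpose for death. A subject with visits after the imputed date was alive on that date, so the result contradicts the database.

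The two SAP rules also rank information the wrong way round. A wholly unknown death date is kept after the last contact, while one known to the month or year can fall before it.

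Two analyses are exposed. Overall survival is plotted by Kaplan-Meier for each subject status and uses the date of death directly. In section 7.2.3 the date of death is also one of the events that end the infection and hospitalization observation periods.

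**Working it through.** The documents give no figure to reproduce: no sample size, number of deaths or number of partial dates. The check applies the section 14 branches to example dates and compares the result with the section 7.2.3 rule. All calendar dates and group sizes below are assumptions.

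**Formula (SAP 7.2.3).** Overall survival (OS) = date of death − date of treatment initiation + 1. The comparator date of death is the last available date + 1 day.

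**Cases.** Registry first dose is 10 Mar 2020 throughout. In case E the STP-2279-002 first dose is 1 Jun 2016.

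| Case | Death recorded as | Last assessment | Imputed by section 14 | OS, section 14 | OS, 7.2.3 rule | Imputed death precedes last assessment by |
|---|---|---|---|---|---|---|
| A | 2020 | 20 Sep 2020 | 10 Mar 2020 | 1 | 196 | 194 days |
| B | 2021 | 20 Sep 2021 | 1 Jan 2021 | 298 | 561 | 262 days |
| C | Sep 2020 | 20 Sep 2020 | 1 Sep 2020 | 176 | 196 | 19 days |
| D | Mar 2020 | 25 Mar 2020 | 10 Mar 2020 | 1 | 17 | 15 days |
| E (STP-2279-002) | 2020 | 20 Sep 2020 | 10 Mar 2020 | 1379 | 1574 | 194 days |

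Cases A and D land on Day 1. Case E does not, because the date is imputed to the registry start while OS runs from the earlier study. The imputed death still precedes the last assessment.

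**Largest backward shift from the true date.** With the month known it is 30 days (31st moved to 1st). With only the year known it is 364 days, or 365 in a leap year (31 December moved to 1 January, or to a first dose on 1 January).

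**Effect on the Kaplan-Meier curve.** Take one death among N subjects, imputed to Day 1, with no other deaths. From Day 1 to the true date the curve reads 1 − 1/N instead of 1. After the true date the correct value is 1 − 1/R, where R is the number still at risk at that time.

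| N | Level if placed at Day 1 | Correct later level, none censored | Correct later level, some censored |
|---|---|---|---|
| 5 | 1 − 1/5 = 0.800 | 0.800 | R = 3: 0.667 |
| 10 | 1 − 1/10 = 0.900 | 0.900 | R = 7: 0.857; R = 5: 0.800 |
| 30 | 1 − 1/30 = 0.967 | 0.967 | R = 21: 0.952; R = 15: 0.933 |

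Early survival is understated. The later level is unchanged if nobody is censored in between, and overstated if some are.

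**Effect on observation periods.** Assume no other end event, such as last dose + 30 days, comes first.

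- Case A: the first-year period contributes 1 day instead of 196.
- Case B: the first-year period contributes 298 days instead of 365. The second-year period (Study Days 366 to 730) contributes none instead of 561 − 366 + 1 = 196, so the subject leaves that denominator.

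**The case against.** The strongest reply is that this will seldom happen. Protocol section 10.8.4 asks for the date of death to be recorded and for deaths to be reported immediately. Protocol section 7.7 has deaths notified to the monitoring committee with supporting documents. Protocol section 14.7.1 provides for manual queries on discrepant information, which could catch a death dated before later visits. The commoner gap is likely to be a missing day, where the shift is at most 30 days. Survival is descriptive, no hypothesis is tested, and the listings show the partial date. All of this stands and limits the practical weight. It does not make the rule right, since the SAP itself provides for partial death dates.

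A second reply is that section 7.2.3 may already cover the case, because a partial date could be read as an unknown one. The wording leaves room for that. But section 14 gives partial dates their own line, so a programmer would more naturally follow section 14. On either reading the two sections need reconciling.

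A reader might infer that one mis-dated death lowers survival by 1/N, or 3.3% with 30 at risk to 20% with 5. The documents do not support that as a measure of the distortion. A step of 1/N is what any single death produces with N at risk. Misdating moves the step earlier, and the later level changes only through intervening censoring. The group sizes are also not in the documents.

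**Conclusion.** The rule is wrong as written. Followed literally, it dates some deaths to first dose and others before visits already recorded, and it conflicts with section 7.2.3. Each affected death is moved back by at most 30 days when the month is known and by up to 364 or 365 days when only the year is known. The Kaplan-Meier step comes too early, and the infection and hospitalization observation time can be cut short.

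The OS of 1 day is confined to Adagen-naïve and Adagen-transitioning subjects with a year-only death in the first-dose year or a day-missing death in the first-dose month. A reader might extend it to every group, but STP-2279-002 participants have an earlier OS origin and generally do not land on Day 1.

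Nor do the documents show that any reported curve is affected, because they do not say how many deaths or partial dates there are. The point rests on the SAP text alone; the example dates and group sizes only illustrate it.

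**What to change.** In SAP section 14, replace the line on partial death dates with wording such as:

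> A partial death date is set to the later of (a) the first day of the known month or year and (b) the day after the last available date in the database, as used in Section 7.2.3, but not later than the end of the known month or year. If the last available date falls after that month or year, the record is queried.

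In section 7.2.3, state that its rule applies to completely unknown death dates.

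This keeps the anchor the SAP already uses. In the examples it gives OS of 196 (A), 561 (B), 196 (C), 17 (D) and 1574 (E) days. The cost is one replaced sentence, one clarification and a small change to the death-date derivation, with no new data.

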APPENDIX A: SCORING THE SF-36V1

The SF-36v1 consists of 36 questions covering 8 health domains: physical functioning, bodily pain, role limitations due to physical problems, role limitations due to emotional problems, general health perceptions, mental health, social function, and vitality. The SF-36v1 will be scored for the 8 sub-domains according to the standard SF-36v1 scoring algorithms (0 to 100 scale) according to Table 1.

In the event that data is missing for an individual item from the domains of the SF-36v1 Health Status Survey, the average value of the completed items in the corresponding domain will be used as an estimate of the missing item. If more than 50 percent of the items from a domain are missing for an individual questionnaire, the corresponding deficient domain(s) will be excluded from analyses. For example, if only 3 of the 5 general health questions are answered, the mean of those 3 answers will be used to fill in the responses of the remaining 2 general health questions. However, if only 1 or 2 general health questions are answered, the general health score would be set to missing.

Scale	Item	Coding	Range of Raw Score	Normalization*
Physical functioning	Items 3a to 3j	Yes, limited a lot = 1	10-30	(S-10)/20 × 100
		Yes, limited a little = 2		
		No, not limited = 3		
Role-physical	Items 4a to 4d	All of the time = 1	4-20	(S-4)/16 × 100
		Most of the time = 2		
		Some of the time = 3		
		A little of the time = 4		
		None of the time = 5		
Bodily pain	Item 7	None = 6	2-12	(S-2)/10 × 100
		Very mild = 5.4		
		Mild = 4.2		
		Moderate = 3.1		
		Severe = 2.2		
		Very severe=1		

Table 1. Coding and Scoring for the 8 SF-36 (Version 1) Scales

Scale	Item	Coding	Range of Raw Score	Normalization*
	Item 8 if both items 7 and 8 are answered	Not at all and item7 equals 'None' = 6		
		Not at all and item7 not equal 'None' = 5		
		A little bit = 4		
		Moderately = 3		
		Quite a bit = 2		
		Extremely = 1		
	Item 8 if item 7 is not	Not at all = 6		
	answered	A little bit = 4.75		
		Moderately =3.5		
		Quite a bit = 2.25		
		Extremely = 1		
General health	Item 1	Excellent = 5	5-25	(S-5)/20 × 100
		Very good = 4.4		
		Good = 3.4		
		Fair = 2		
		Poor = 1		
	Items 11a and 11c	Definitely true = 1		
		Mostly true = 2		
		Don't know = 3		
		Mostly false = 4		
		Definitely false = 5		
	Items 11b and 11d	Definitely true = 5		
		Mostly true = 4		
		Don't know = 3		
		Mostly false = 2		
		Definitely false = 1		
Vitality	Items 9a and 9e	All of the time = 5	4-20	(S-4)/16×100
		Most of the time = 4		
		Some of the time = 3		
		A little of the time = 2		
		None of the time = 1		

Scale	ltem	Coding	Range of Raw Score	Normalization*
	Items 9g and 9i	All of the time = 1		
		Most of the time = 2		
		Some of the time = 3		
		A little of the time = 4		
		None of the time = 5		
Social functioning	Item 6	Not at all = 5	2-10	(S-2)/8 × 100
		Slightly = 4		
		Moderately = 3		
		Quite a bit = 2		
		Extremely = 1		
	Item 10	All of the time = 1		
		Most of the time = 2		
		Some of the time = 3		
		A little of the time = 4		
		None of the time = 5		
Role-emotional	Items 5a to 5c	All of the time = 1	3-15	(S-3)/12 × 100
		Most of the time = 2		
		Some of the time = 3		
		A little of the time = 4		
		None of the time = 5		
Mental health	Items 9b, 9c and 9f	All of the time = 1	5-25	(S-5)/20 × 100
		Most of the time = 2		
		Some of the time = 3		
		A little of the time = 4		
		None of the time = 5		
	Items 9d and 9h	All of the time = 5		
		Most of the time = 4		
		Some of the time = 3		
		A little of the time = 2		
		None of the time = 1		

S = raw score = sum of item scores after coding

APPENDIX B: SCORING THE PADQOL-16 QUESTIONNAIRE

The questions will be combined to 7 scales and to a total score as follows (Ballow et al., 2017):

Abbreviation	Meaning	Question
GH	General health	(1) I get infections between infusions.
		(5) I have to seek unscheduled medical visits for my PIDD.
		(7) I have trouble with infections.
VT	Vitality	(2) I am more tired than normal.
		(10) I struggle to keep up with others.
PF	Physical functioning	(3) My cough has worsened.
		(4) I have flare-ups and symptoms of sinusitis.
		(8) The effects of my treatment wear off between infusions.
		(9) I have trouble with shortness of breath.
RP	Role (physical)	(6) I have nausea and bloating.
		(13) I have missed school or work due to my PIDD.
RE	Role (emotional)	(11) I have trouble sleeping.
		(14) I feel that I am a burden to others.
МН	Mental health	(12) I feel downhearted and depressed about my PIDD.
SF	Social functioning	(15) I require help from others frequently.
		(16) I avoid certain places and situations because of my PIDD.

Each question will be scored as follows and sumed for each of the scales above:

Rarely/Never = 0

Sometimes = 1

Often/always = 2.

Each scale will be standardized to a range of 0 to 100 by the following equation:

Standardized scale=raw scale*50/number of questions.

The total scale includes all questions and will be calculated in the same way as the subscales. The sub-scales will only be calculated if all questions of the sub-scale are available. The total scale will be calculated if 15 or more questions are answered. The total scale will be standardized as follows:

Standardized total scale=raw scale*50/number of questions answered.

APPENDIX C: STANDARDIZED UNITS FOR PRESENTING THE LABORATORY VALUES

For the statistical analysis and all tables and listings, the laboratory values will be converted to and reported by the following standardized units:

LBTESTCD	LBTEST	LBCAT	Unit
ALB	Albumin	CHEMISTRY	g/dL
ALP	Alkaline Phosphatase	CHEMISTRY	U/L
ALT	Alanine Aminotransferase	CHEMISTRY	U/L
AST	Aspartate Aminotransferase	CHEMISTRY	U/L
BICARB	Bicarbonate	CHEMISTRY	mEq/L
BILI	Bilirubin	CHEMISTRY	mg/dL
CA	Calcium	CHEMISTRY	mg/dL
CL	Chloride	CHEMISTRY	mEq/L
CREAT	Creatinine	CHEMISTRY	mg/dL
GLUC	Glucose	CHEMISTRY	mg/dL
Κ	Potassium	CHEMISTRY	mEq/L
MG	Magnesium	CHEMISTRY	mg/dL
PHOS	Phosphate	CHEMISTRY	mg/dL
PROT	Protein	CHEMISTRY	g/dL
SODIUM	Sodium	CHEMISTRY	mEq/L
UREAN	Urea Nitrogen	CHEMISTRY	mg/dL
BASO	Basophils	HEMATOLOGY	10^9/L
BASOLE	Basophils/Leukocytes	HEMATOLOGY	%
EOS	Eosinophils	HEMATOLOGY	10^9/L
EOSLE	Eosinophils/Leukocytes	HEMATOLOGY	%
НСТ	Hematocrit	HEMATOLOGY	%
HGB	Hemoglobin	HEMATOLOGY	g/dL

LYM	Lymphocytes	HEMATOLOGY	10^9/L
LYMLE	Lymphocytes/Leukocytes	HEMATOLOGY	%
MONO	Monocytes	HEMATOLOGY	10^9/L
MONOLE	Monocytes/Leukocytes	HEMATOLOGY	%
NEUT	Neutrophils	HEMATOLOGY	10^9/L
NEUTLE	Neutrophils/Leukocytes	HEMATOLOGY	%
PLAT	Platelets	HEMATOLOGY	10^9/L
WBC	Leukocytes	HEMATOLOGY	10^9/L
IGA	Immunoglobulin A	IMMUNOLOGY	g/L
IGG	Immunoglobulin G	IMMUNOLOGY	g/L
IGM	Immunoglobulin M	IMMUNOLOGY	g/L
BACT	Bacteria	URINALYSIS	/HPF
GLUC	Glucose	URINALYSIS	mg/dL
KETONES	Ketones	URINALYSIS	mg/dL
PROT	Protein	URINALYSIS	mg/dL
RBC	Erythrocytes	URINALYSIS	/HPF
UROBIL	Urobilinogen	URINALYSIS	mg/dL
WBC	Leukocytes	URINALYSIS	/HPF

Document Name: Revcovi Registry SAP V4.0 06June2023 UBC signed

Document Type: Analysis Plan

Signer	Reason for Signature	Signer Comments	Signature Status	Date Signed	Date Removed
[name] (UBC)	Reviewer		Signed	06-Jun-2023 02:31:14 PM GMT	
[name] (UBC)	Author		Signed	06-Jun-2023 02:27:54 PM GMT
